5.4.3 Reporting Requirements for Pregnancies

5.4.3.1 Pregnancies in Female Partners of Male Subjects

Although embryo-fetal development studies are not available, condom use will not be required in male subjects enrolled in the study because the margin between the minimal anticipated biological effect level plasma concentration (7 ng/mL) and the estimated maternal C_{max} (at a single SC dose of 1 mg/kg) is greater than 10-fold (Banholzer et al. 2012). At this time, very little emicizumab is thought to transfer into semen, and there are no known reproductive risks to female partners of male subjects treated with emicizumab, so contraception use by male subjects is not required for participation in the study. Therefore, no proactive collection of pregnancy information for female partners of male subjects treated with emicizumab will be required.

5.5 FOLLOW-UP OF HEALTHY SUBJECTS AFTER ADVERSE EVENTS

5.5.1 Investigator Follow-Up

The investigator should follow each adverse event until the event has resolved to baseline grade or better, the event is assessed as stable by the investigator, the subject is lost to follow-up, or the subject withdraws consent. Every effort should be made to follow all serious adverse events considered to be related to study drug or trial-related procedures until a final outcome can be reported.

During the study period, resolution of adverse events (with dates) should be documented on the Adverse Event eCRF and in the subject's medical record to facilitate source data verification. If, after follow-up, return to baseline status or stabilization cannot be established, an explanation should be recorded on the Adverse Event eCRF.

5.5.2 Sponsor Follow-Up

For serious adverse events, non-serious adverse events of special interest, and pregnancies, the Sponsor or a designee may follow up by telephone, fax, electronic mail, and/or a monitoring visit to obtain additional case details and outcome information (e.g., from hospital discharge summaries, consultant reports, autopsy reports) in order to perform an independent medical assessment of the reported case.

5.6 POST-STUDY ADVERSE EVENTS

The Sponsor should be notified if the investigator becomes aware of any serious adverse event that occurs after the end of the adverse event reporting period (defined as 16 weeks after the last subject dosing of study drug), if the event is believed to be related to prior study drug treatment. These events should be reported through use of the Adverse Event eCRF. However, if the electronic data capture (EDC) system is not available, the investigator should report these events directly to the Sponsor or its designee, either by faxing or by scanning and e-mailing the Serious Adverse Event/Adverse Event of Special Interest Reporting Form with use of the fax number or e-mail address provided to investigators.

5.7 EXPEDITED REPORTING TO HEALTH AUTHORITIES, INVESTIGATORS, INSTITUTIONAL REVIEW BOARDS, AND ETHICS COMMITTEES

The Sponsor will promptly evaluate all serious adverse events and non-serious adverse events of special interest against cumulative product experience to identify and expeditiously communicate possible new safety findings to investigators, IRBs, ECs, and applicable health authorities based on applicable legislation.

To determine reporting requirements for single adverse event cases, the Sponsor will assess the expectedness of these events using the following reference document:

- Emicizumab (RO5534262) IB

The Sponsor will compare the severity of each event and the cumulative event frequency reported for the study with the severity and frequency reported in the applicable reference document.

Reporting requirements will also be based on the investigator's assessment of causality and seriousness, with allowance for upgrading by the Sponsor as needed.

6. STATISTICAL CONSIDERATIONS AND ANALYSIS PLAN

The primary objective of this study is to characterize the pharmacokinetic profile of emicizumab in healthy Chinese subjects following single SC administration of emicizumab. Statistical summaries will be descriptive in nature. All subjects who receive any amount of study medication and with at least one post-baseline safety assessment will be included in the safety analysis.

6.1 DETERMINATION OF SAMPLE SIZE

The number of subjects (12 evaluable subjects) is chosen based on practical clinical judgment (AUC and C_{max} variability of emicizumab in Caucasian and Japanese healthy subjects) and China regulatory requirement.

6.2 SUMMARIES OF CONDUCT OF STUDY

The number of subjects who enroll, discontinue, or complete the study will be summarized. Reasons for premature study withdrawal will be listed and summarized. Protocol deviations will be listed and evaluated for their potential impact on interpretation of study results. Study drug administration will be summarized.

6.3 ANALYSIS POPULATIONS

6.3.1 Pharmacokinetic Analysis Population

Subjects will be excluded from the PK analysis population if they deviate significantly from the protocol or if data are unavailable or incomplete which may influence the PK analysis. Excluded cases will be documented together with the reason for exclusion. All decisions on exclusions from the analysis will be made prior to database closure.

6.3.2 Safety Analysis Population

All subjects who have received any amount of study medication, whether prematurely withdrawn from the study or not, and with at least one post-baseline safety assessment, will be included in the safety analysis.

6.3.3 Immunogenicity Analysis Population

The immunogenicity analyses will include subjects with at least one predose and one postdose ADA assessment.

6.4 SUMMARIES OF TREATMENT GROUP

Demographic and baseline characteristics (including age, sex, etc.) will be summarized using means, SDs ranges for continuous variables and proportions for categorical variables, as appropriate.

6.5 PHARMACOKINETIC ANALYSES

Individual plasma concentrations at each sampling timepoint for emicizumab will be presented by listings and appropriate descriptive summary statistics, including arithmetic means, geometric means, medians, minimums-maximums, SDs, and coefficients of variation. Individual and mean plasma concentration versus time data will be plotted on semi-logarithmic scales.

All PK parameters will be presented by individual listings and summary statistics including arithmetic means, geometric means, medians, minimums-maximums, SDs and coefficients of variation.

The primary emicizumab PK study parameters will be the C_{max} and the AUC ($AUC_{0-\infty}$ if it can be derived, otherwise truncated as appropriate). All other PK parameters will be regarded as secondary.

Non-compartmental analysis will be employed for estimation of the following PK parameters:

- t_{max} : Time to maximum observed plasma concentration
- C_{max} : Maximum observed plasma concentration
- $AUC_{0-\infty}$: Area under the plasma concentration-time curve between time zero extrapolated to infinity
- AUC_{0-last} : Area under the plasma concentration-time curve between time zero and the time of the last quantifiable concentration
- $t_{1/2}$: Apparent terminal half-life, computed as $(\ln 2/\lambda_z)$
- CL/F: Apparent clearance
- Vz/F: Apparent volume of distribution
- MRT: Mean residence time

6.6 SAFETY ANALYSES

All safety analyses will be based on the safety analysis population.

6.6.1 Adverse Events

The original terms recorded on the eCRF by the investigator for adverse events will be standardized by the sponsor.

Adverse events will be summarized by mapped term and appropriate thesaurus level.

6.6.2 Clinical Laboratory Test Results

All clinical laboratory data will be stored on the database in the units in which they were reported. Subjects listings and summary statistics at each assessment time will be presented using the International System of Units (SI units; Système International d'Unités). Laboratory data not reported in SI units will be converted to SI units before processing.

Laboratory test values will be presented by individual listings with flagging of values outside the normal ranges.

The proportion of subjects with laboratory abnormalities will be summarized. Additionally, the value and change from baseline for each laboratory test will be summarized by visit using descriptive statistics.

6.6.2.1 Standard Reference Ranges and Transformation of Data

Roche standard reference ranges, rather than the reference ranges of the investigator, will be used for all parameters. For most parameters, the measured laboratory test result will be assessed directly using the Roche standard reference range. Certain laboratory parameters will be transformed to Roche's standard reference ranges.

A transformation will be performed on certain laboratory tests that lack sufficiently common procedures and have a wide range of investigator ranges, e.g., enzyme tests that include AST, ALT, alkaline phosphatase, and total bilirubin. Since the standard reference ranges for these parameters have a lower limit of zero, only the upper limits of the ranges will be used in transforming the data.

6.6.2.2 Definition of Laboratory Abnormalities

For all laboratory parameters included, there exists a Roche predefined standard reference range. Laboratory values falling outside this standard reference range will be labeled "H" for high or "L" for low in subject listings of laboratory data.

In addition to the standard reference range, a marked reference range has been predefined by Roche for each laboratory parameter. The marked reference range is broader than the standard reference range. Values falling outside the marked reference range that also represent a defined change from baseline will be considered marked laboratory abnormalities (i.e., potentially clinically relevant). If a baseline value is not available for a subject, the midpoint of the standard reference range will be used as the subject's baseline value for the purposes of determining marked laboratory abnormalities. Marked laboratory abnormalities will be labeled in the subject listings as "HH" for very high or "LL" for very low.

6.6.3 Vital Signs

Vital signs data will be presented by individual listings with flagging of values outside the normal ranges and flagging of marked abnormalities. In addition, tabular summaries will be used, as appropriate.

6.6.4 ECG Data Analysis

ECG data will be presented by individual listings with flagging of values outside the normal ranges and flagging of marked abnormalities. In addition, tabular summaries will be used, as appropriate.

6.6.5 Concomitant Medications

The original terms recorded on the subjects' eCRF by the investigator for concomitant medications will be standardized by the sponsor by assigning preferred terms.

Concomitant medications will be presented in summary tables and listings.

6.7 IMMUNOGENICITY ANALYSES

The numbers and proportions of ADA-positive subjects and ADA-negative subjects will be summarized. Subjects are considered to be ADA positive if they are ADA negative at baseline but develop an ADA response following study drug administration (treatment-induced ADA response), or if they are ADA positive at baseline and the titer of one or more post-baseline samples is at least 4-fold greater than the titer of the baseline sample (treatment-enhanced ADA response). Subjects are considered to be ADA negative if they are ADA negative at baseline and all post-baseline samples are negative, or if they are ADA positive at baseline but do not have any post-baseline samples with a titer that is at least 4-fold greater than the titer of the baseline sample (treatment unaffected).

The relationship between ADA status and safety and PK results will be analyzed and reported descriptively via subgroup analyses.

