human immunoglobulin G antibodies. Furthermore, comparison of PK profiles between Japanese and Caucasian healthy subjects did not reveal racial differences. Similar PK profiles were observed in healthy Japanese subjects following abdominal SC injection of 1 mg/kg with two different emicizumab formulations (G1 [80 mg/mL] and G2.1 [150 mg/mL]). Also, similar PK profiles were observed following SC injections in abdomen, upper arm, and thigh, which suggest that emicizumab can be interchangeably injected in each of these three locations. In addition, emicizumab was almost completely absorbed following SC injection, with an absolute bioavailability of 80.4%–93.1%, depending on the injection site. In patients with hemophilia A, emicizumab trough plasma concentrations increased in a dose-proportional manner with weekly dosing to achieve a plateau after approximately 12 weeks in the first two dosing groups, in which a loading dose was administered, and after approximately 24 weeks in the highest dose group, in which no initial loading dose was administered.

In the Phase I/II studies ACE001JP, ACE002JP, and JP29574, emicizumab has been administered to 108 healthy subjects and 18 patients with hemophilia A. A total of 10 subjects/patients tested positive for anti-drug antibodies (ADAs) on at least one occasion. Seven subjects/patients developed an ADA after exposure, and in 3 other patients, ADA was detected before first exposure to emicizumab. No clinically relevant changes in the pharmacokinetics and pharmacodynamics of emicizumab have been detected in any of the hemophilia A patients who tested positive for ADA (i.e., none of the ADA have been neutralizing), and the presence of ADA did not have an effect on the annualized bleeding rate reduction in these patients.

Based on these compelling Phase I/II data, a clinical development program in adult and pediatric patients with hemophilia A (both with and without FVIII inhibitors) has been initiated. See the IB for additional details on clinical studies with emicizumab.

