3.4.2 Safety Outcome Measures

The safety outcome measures for this study are as follows:

- Incidence and severity of adverse events
- Incidence and clinical significance of anti-emicizumab antibodies
- Laboratory test data (hematology, blood chemistry, coagulation screening test, urinalysis, viral serology, and immunology), vital signs, 12-lead ECG
- Coagulation tests

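### Section 6.7 counts subjects with pre-existing, unboosted ADA as ADA negative, and no other ADA status is defined for the PK and safety subgroups

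*Combined protocol and SAP*

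**What the plan says.** Section 6.7 recognises two ADA categories, and its summary is built on them: "The numbers and proportions of ADA-positive subjects and ADA-negative subjects will be summarized". The positive category holds treatment-induced and treatment-enhanced responses. The negative category has two limbs. The first is subjects with no ADA in any sample: "Subjects are considered to be ADA negative if they are ADA negative at baseline and all post-baseline samples are negative". The second, labelled treatment unaffected, applies "if they are ADA positive at baseline but do not have any post-baseline samples with a titer that is at least 4-fold greater" than the baseline sample.

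The next paragraph of Section 6.7 puts the classification to a second use: "The relationship between ADA status and safety and PK results will be analyzed and reported descriptively via subgroup analyses".

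Section 6.3.3 does not remove baseline-positive subjects: "The immunogenicity analyses will include subjects with at least one predose and one postdose ADA assessment". Section 3.4.2 lists among the safety outcomes "Incidence and clinical significance of anti-emicizumab antibodies". Section 1.2.2 shows that pre-existing ADA has occurred in this programme: "in 3 other patients, ADA was detected before first exposure to emicizumab".

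Appendix 1 schedules ADA samples at three times: predose on Day 1, Day 57 and Day 113.

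**The concern.** The two uses ask different questions. Incidence asks whether dosing provoked or boosted an antibody response, and for that it is correct to set aside pre-existing, unboosted ADA. The PK and safety subgroups ask whether having ADA goes with different exposure or more events. For that question, a subject known to carry ADA at dosing does not belong with subjects who never had any.

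Section 6.7 defines no third status, so its rule puts him there. Two things follow. The contrast between subgroups is pulled toward no difference if pre-existing ADA affects exposure. And a low concentration profile or a hypersensitivity reaction in him would be tabulated against an ADA-negative subject, although the clinical significance of ADA is a listed outcome.

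The sampling schedule adds to this. Apart from an early-termination visit (Appendix 1, footnote a) or an unscheduled sample after a reaction (Table 1), the predose sample is the only ADA result before Day 57. For baseline-positive, unboosted subjects, the rule sets aside the only scheduled ADA information on early exposure.

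There is also a small loss of comparability. The earlier total of 10 ADA-positive people in Section 1.2.2 includes the three positive before exposure. Section 6.7 would count such a person as positive only after a 4-fold titer rise.

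**Working it through.** The plan gives no figure on this point, so there is none to reproduce. The check has three parts.

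**1. Where each kind of subject falls under Section 6.7**

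| Baseline | After dosing | Label |
|---|---|---|
| Negative | All negative | Negative |
| Negative | Any ADA response | Positive (induced) |
| Positive | Titer at least 4-fold above baseline | Positive (enhanced) |
| Positive | No such rise, including a change to negative | Negative (unaffected) |

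The first and last rows share a label. Nothing in Sections 6.3.3 or 6.7 separates them again before the subgroup analyses.

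**2. How likely such a subject is**

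Inputs from Section 1.2.2:
- "emicizumab has been administered to 108 healthy subjects and 18 patients with hemophilia A". The healthy count agrees with the study descriptions: 48 + 60 = 108. The total is 108 + 18 = 126.
- ADA positives: 7 after exposure + 3 before exposure = 10.

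Planned size (Section 4.3): 16 enrolled, at least 12 evaluable. With rate p, the chance of at least one case among N is 1 − (1 − p)^N.

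- Pooled rate p = 3/126 = 2.4% (exact two-sided 95% interval 0.5% to 6.8%).
  - N = 16: 1 − (123/126)^16 = 32% (7.6% to 67.6% over the interval); expected number 16 × 3/126 = 0.38.
  - N = 12: 1 − (123/126)^12 = 25%; expected number 0.29.
- All three were hemophilia patients: the healthy-subject rate is 0/108, with two-sided 95% upper limit 1 − 0.025^(1/108) = 3.4%.
  - N = 16: from 0% to 1 − 0.025^(16/108) = 42%.

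For comparison, treatment-induced ADA at 7/126 = 5.6% gives 16 × 7/126 = 0.9 expected cases. The ADA-positive subgroup is itself likely to hold very few subjects.

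**3. How far the subgroup contrast moves**

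Let r be the true ratio of geometric mean exposure, ADA carriers to never-positive subjects. Assume it is the same for pre-existing and treatment-emergent ADA. If k pre-existing cases sit in a comparator of m, the comparator's geometric mean is multiplied by r^(k/m), so the observed ratio is r^(1 − k/m).

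With k = 1 and one treatment-emergent subject, m is 15 (of 16) or 11 (of 12). The values of r are illustrative; the documents give none.

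| Assumed r | m = 15 | m = 11 |
|---|---|---|
| 0.5 | 0.524 | 0.533 |
| 0.7 | 0.717 | 0.723 |
| 0.8 | 0.812 | 0.816 |

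Taking the unaffected subject out of the comparator makes k = 0 and returns r.

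**The case against.** The strongest reply is that this is unlikely to matter. Section 1.2.2 calls the three pre-exposure cases patients, while it calls the seven later cases subjects or patients. Read literally, no healthy volunteer had pre-existing ADA, and this trial enrols only healthy volunteers. The same section reports no clinically relevant PK or PD change in any ADA-positive hemophilia patient and says none of the ADA were neutralizing. The analysis is descriptive (Section 6), and Section 6.5 promises individual listings and plots, so an odd profile among 16 subjects would be seen. Section 6.7 also never says that the subgroups use the two-way label, and it already names the unaffected response.

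Much of this stands, and it limits the size. It does not remove the point. The two-way label is the only ADA status the section defines. No ADA listing is promised, so a reader of the PK plots would not know which profile belonged to a baseline-positive subject.

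Four stronger readings are tempting, and the documents do not support them.
- A reader might infer bias in the primary PK results. One subject at half the usual exposure would lower a 16-subject geometric mean by about 4% (0.5^(1/16) − 1 = −4.2%). But Section 6.5 does not split those summaries by ADA status, so the shift is the same whatever his label.
- A reader might infer that these subjects carry ADA throughout exposure. The unaffected limb also holds subjects who turn negative, and persistence between the three samples is not observed.
- A reader might infer that Cmax is especially affected because it occurs within a set early period. The documents give no human time to Cmax; the only values, 3.00–5.33 days in Section 1.2.1, are from monkeys.
- A reader might infer that the rule empties the ADA-positive subgroup. It removes no treatment-induced or treatment-enhanced subject.

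**Conclusion.** The point holds as a minor one, conditional on enrolment. Section 6.7 uses a definition suited to treatment-emergent incidence where the presence of ADA is what matters, and a subject with pre-existing ADA would be analysed in the comparator.

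The expected number of such subjects is 0 or 1, and the data cannot say whether the true chance is near zero or several tenths. Even with exposure assumed halved, the dilution is only 0.02 to 0.03 on the ratio scale. The more practical harm is misattribution: with about one treatment-induced case expected, a baseline-positive subject could be the only ADA carrier in the study and would be reported as negative.

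The calculation rests on the earlier counts applying here, on the illustrative ratios, and on pre-existing and treatment-emergent ADA having the same effect. Sample size, the primary PK summaries and the incidence definition are unaffected.

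**What to change.** Keep the current definition for ADA incidence. Add two sentences to Section 6.7 to this effect: for the PK and safety analyses, never-positive subjects (negative in every sample, including baseline) are compared with treatment-induced or treatment-enhanced subjects; subjects with pre-existing, treatment-unaffected ADA are reported separately, listed individually and marked on the PK plots.

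With 0 or 1 such subjects expected, the listing and marking are enough, and a full third column of summary statistics is not needed.

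The change needs no new samples or visits. Its cost is one more category to report, probably very small or empty. It should be made before the ADA results are seen.

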7. DATA COLLECTION AND MANAGEMENT

7.1 DATA QUALITY ASSURANCE

The Sponsor will be responsible for data management of this study, including quality checking of the data. Sites will be responsible for data entry into the EDC system.

A comprehensive validation check program will verify the data. Discrepancies will be generated automatically in the system at the point of entry or added manually for resolution by the investigator.

The Sponsor will produce a Data Handling Manual that describes the quality checking to be performed on the data. Laboratory electronic data will be sent directly to the Sponsor, using the Sponsor's standard procedures to handle and process the electronic transfer of these data.

System backups for data stored by the Sponsor and records retention for the study data will be consistent with the Sponsor's standard procedures.

